### 9.2. Derived and transformed data

#### 9.2.1. Baseline and demographic derivations

The age of the subject in years will be determined using the date of birth (recorded at screening) and the date of consent. Since year only is being collected for this study, age will be calculated as the difference between the year of the screening visit and date of birth as:

- Year of consent – year of birth + 1.

Time since CAH diagnosis will be determined using the date of CAH diagnosis captured in the electronic case record form (eCRF) and will be calculated as:

- Date of randomisation – date of CAH diagnosis + 1 / 365.25.

In the derivation of age at study entry and time since CAH diagnosis partial dates will be handled as described in Section 9.1.

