## 9.2 Inclusion Criteria

1. Known CAH due to 21-hydroxylase deficiency (classic CAH) diagnosed in childhood with documented (at any time) elevated 17-OHP and/or A4 and currently treated with hydrocortisone, prednisone, prednisolone or dexamethasone (or a combination of the aforementioned glucocorticoids) on a stable glucocorticoid therapy for a minimum of 6 months.
2. Male or female subjects aged 18 and above.
3. Provision of signed written informed consent.
4. Non-pregnant, non-lactating females who are:
  - a. Post menopausal (defined as at least 12 months natural spontaneous amenorrhoea or at least 6 weeks following surgical menopause, i.e. bilateral oophorectomy)
  - b. Naturally or surgically sterile (hysterectomy, bilateral oophorectomy, bilateral tubal ligation with surgery at least 6 weeks prior to study initiation)
  - c. Of childbearing potential with a negative urinary pregnancy test and using a medically acceptable method of contraception (see Section 11.7 for details)

Note: females presenting with oligomenorrhoea or amenorrhoea who are aged  $\leq 55$  years of age should be considered potentially fertile and therefore, as well as undergoing pregnancy testing like all other female subjects, will be expected to be using an acceptable method of contraception as noted above.

5. PRA less than 1.5 times ULN at screening or within 3 months prior to screening, except in subjects who have been diagnosed with hypertension where the renin is not being used to monitor fludrocortisone replacement.

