## 9. Data handling conventions

### 9.1. Premature withdrawal and missing data

Missing 17-OHP and A4 values (including those considered missing due to being taken outside the permitted time window) within the 24-hour hormone profile will be imputed by linear interpolation of the two closest non-missing measurements to the scheduled missing time point (including out-of-window measurements). Further details are given in Section 9.3.3. In the event that several values are missing from a single profile, a decision will be made about the validity of the whole profile at the Data Review Meeting on a case-by-case basis.

For efficacy analyses based on the Week 12 and Week 24 visits, subjects who have withdrawn from the study will be assessed on the basis of the latest available 24-hour profile. This is a conservative procedure as subjects enter the study already receiving a suitable dose of their standard therapy.

When calculations must be based upon incomplete dates the following process will be used. If year is missing do not impute. The value should be considered missing. If year is populated but both month and day are missing then the date defaults to 1st July. If day only is missing then the day defaults to the 15th of the month.

For adverse events and concomitant medications, if year is missing do not impute. If start year is populated but both month and day are missing, or if month is missing and day is present, then the date defaults to 1st January. If day only is missing then the day defaults to the 1st of the month. If end year is populated but both month and day are missing, or if month is missing and day is present, then the date defaults to 31st December. If day only is missing then the day defaults to last day of the month. For definition of treatment emergent and ongoing, if partial dates are only available for start and end, then we are conservative and assume treatment emergent/ongoing.

For those subjects with one middle dose then this is considered as “middle 1”, and middle2 is blank for all subjects except those with a second middle dose.

Exploratory and sensitivity analyses will be performed to assess the effect of any missing data on the efficacy conclusions. This will be discussed at the Data Review Meeting and a decision will be made on the appropriate analyses.

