### 10.3. Demographic and baseline characteristics

The following demographic and baseline characteristics will be summarised and listed at the screening visit: age (calculated in whole years), gender, race, ethnicity, height, weight, BMI, waist circumference. Age will be split into four groups and will be included in the demographic and baseline characteristics summary table. The following age groups will be displayed:

- $\geq 18$  -  $< 30$
- $\geq 30$  -  $< 50$
- $\geq 50$  -  $< 70$
- $\geq 70$

Baseline disease characteristics including time since CAH diagnosis, whether the subject was hospitalized in the last year due to CAH, the number of adrenal crises in the past year and prior CAH medications will be summarised and detailed listings will be produced.

Congenital adrenal hyperplasia medical history, other medical history excluding CAH related events and prior medications will each be summarised and detailed listings will be produced. Mutation status will also be listed.

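### The SAP age formula overstates completed age by 1 or 2 years for every subject and conflicts with a second age rule; two other date formulas are also wrong as printed

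*SAP*

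**What the plan says.** SAP 9.2.1 names date of birth and date of consent as the inputs for age and notes that only the year is collected. It then says that "age will be calculated as the difference between the year of the screening visit and date of birth", and displays the formula "Year of consent – year of birth + 1". Two lines later it adds: "In the derivation of age at study entry and time since CAH diagnosis partial dates will be handled as described in Section 9.1". The rule in SAP 9.1 opens with "When calculations must be based upon incomplete dates the following process will be used" and sets a date with a known year but no month or day to 1 July.

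SAP 10.3 lists "age (calculated in whole years") among the characteristics to be tabulated and continues: "Age will be split into four groups and will be included in the demographic and baseline characteristics summary table". The cut-points are 30, 50 and 70. Protocol 9.2 admits "Male or female subjects aged 18 and above".

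Time since CAH diagnosis, also in SAP 9.2.1, is given as "Date of randomisation – date of CAH diagnosis + 1 / 365.25". SAP 11.1 reports exposure in days and defines total treatment duration as the date of first dose minus the date of last dose, plus 1.

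**The concern.** The sentence on age describes a plain difference, and the formula below it adds 1. Adding 1 is right for an inclusive count of days, as in the study-day formula of SAP 9.3.1. It is not right for a difference of calendar years, which already equals or exceeds completed age. The result looks plausible, so the error could reach the demographic table and the age bands unnoticed.

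The link to SAP 9.1 makes it worse. A year-only subtraction needs no month or day, whereas a birth date set to 1 July, taken with the date of consent, is a complete way to derive age. The section therefore holds two age rules that give different answers, and two programmers could each follow the SAP and disagree.

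The other two formulas, taken literally, give impossible values in the baseline disease and exposure tables.

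**Working it through.** **Inputs.** Age formula, partial-date link and time since diagnosis: SAP 9.2.1. The 1 July default: SAP 9.1. Age bands: SAP 10.3. Entry age: Protocol 9.2. Duration formula: SAP 11.1. Illustrative last dose on Day 169, the target day of Visit 4: SAP Table 6.

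**Age.** Let D = year of consent − year of birth. Completed age is D if the birthday has been reached by consent, and D − 1 if not. The printed formula D + 1 is therefore completed age + 1 or completed age + 2, and never completed age itself. This needs no assumption about the age distribution. For an 18-year-old it gives 19 or 20.

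To size it, take every combination of birth day and consent day in two 365-day years, all equally likely. The birthday has been reached in (365 × 366 / 2) / 365² = 66,795 / 133,225 = 50.1% and not reached in 49.9%. Error against completed age:

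| Rule | −1 | 0 | +1 | +2 | Mean |
|---|---|---|---|---|---|
| D + 1 (as printed) | – | – | 50.1% | 49.9% | +1.50 |
| D (plain difference) | – | 50.1% | 49.9% | – | +0.50 |
| Whole years from 1 July of birth year to consent | 12.4% | 75.0% | 12.6% | – | about 0 |

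Two examples:
- Born October 1990, consent March 2016, completed age 25: printed formula 27, plain difference 26, 1 July rule 25.
- Born February 1999, consent March 2017, completed age 18: printed formula 19, plain difference 18, 1 July rule 17.

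**Age bands.** The added 1, taken alone, moves exactly the subjects with D = 29, 49 or 69. If exact ages were spread evenly from 18 to 60, each such value of D would hold 1/42 of subjects and 69 would not occur, so 2/42 = 4.8% would move. Nine assumed distributions were tried: uniform 18–60, 18–70 and 18–80; and normal, cut off below 18, with mean and SD 28, 6; 30, 8; 35, 10; 35, 12; 40, 12; 45, 12. The share moved is 4.8% to 6.9%, or 0.048 × 120 = 5.8 to 0.069 × 120 = 8.3 of 120 subjects. These are not limits. Uniform 18–28 gives 0%, and a normal with mean 29 and SD 4 gives about 10%.

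**Time since diagnosis.** Take a 30-year history: 30 × 365.25 = 10,957.5 days. As printed, only the 1 is divided: 10,957.5 + 1/365.25 = 10,957.503, which is in days. With brackets: (10,957.5 + 1)/365.25 = 30.003 years.

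**Treatment duration.** First dose Day 1, last dose Day 169. As printed: 1 − 169 + 1 = −167. With the dates in order: 169 − 1 + 1 = 169 days. The printed formula is right only for a one-day exposure (1). It gives 0 for two days and negative values beyond that.

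**The case against.** The best defence has four parts.

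*The slips are obvious.* For time since diagnosis and duration this largely stands. The divisor of 365.25, the stated unit of days and the correctly ordered study-day formula in SAP 9.3.1 make the intent clear, and the impossible values would probably be noticed. It does not stand for age, where a programmer who follows the text exactly gets believable ages.

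*The revision history for SAP version 2.0 records that the age derivation was corrected.* This shows that the formula was looked at. It gives no reason for the added 1 and does not alter the arithmetic.

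*The link to SAP 9.1 is idle, because a year-only subtraction has no incomplete date to fill.* A reader might infer that the link is merely redundant and can be struck out without comment. The text does not support that: it names age expressly, and the 1 July default yields a working derivation. A reader might equally infer that the plain difference is the only sound repair. That is not supported either. Against completed age, the 1 July rule is right in 75% of cases and the plain difference in about 50%. Its drawback is that it can show an eligible 18-year-old as 17, which the plain difference cannot do.

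*Age hardly matters in this trial.* This is broadly true, and it limits the point to a minor correction.

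**Conclusion.** All three formulas are wrong as printed, and age has two conflicting rules. The age excess of 1 or 2 years holds for every subject. The even split and the mean of 1.5 years assume evenly spread birth and consent dates. The 4.8% to 6.9% for band changes is illustrative only, since the documents give no age distribution; it should not be read as an estimate for this trial.

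The consequence is limited to the demographic, baseline disease and exposure summaries. Exposure could also enter the optional episode-level adverse event rates in SAP 11.2, which use patient-years as denominator. The SAP does not say which duration would feed them. Age could enter any exploratory subgroup or baseline-variable analysis added under Protocol 13.9 or SAP 8.5.

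A reader might infer that the primary result or eligibility is affected. The documents do not support this. The ANCOVA adjusts for pre-baseline therapy and the baseline value (SAP 8.2), and the reference ranges in SAP Tables 2 and 3 differ by sex only. Nothing makes the reporting formula the test of the entry age in Protocol 9.2. Power and analysis sets do not change.

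**What to change.** Remove the added 1 and state one age rule, chosen by the sponsor:

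- **Option A:** age = year of consent − year of birth, with age taken out of the sentence that refers to SAP 9.1. It matches the SAP's own description and cannot fall below 18 for an eligible subject. It equals completed age in about 50% of cases and is 1 year high in the rest.
- **Option B:** age = whole years from 1 July of the birth year to the date of consent, keeping the reference to SAP 9.1 and deleting the year-difference sentence and formula. It equals completed age in about 75% of cases and is 1 year low or high in the rest. The table should carry a note that an eligible 18-year-old may appear as 17.

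Then correct the other two:

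- Time since CAH diagnosis (years) = (date of randomisation − date of CAH diagnosis + 1) / 365.25.
- Total treatment duration (days) = date of last dose − date of first dose + 1.

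The cost is three one-line formulas and an edit to the wording around the age rule. No new data are needed, and the primary analysis is untouched.

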### 9.2.2. Derivations of SDS scores

The primary efficacy variable is the natural logarithm of the mean of the 24-hour hormonal profile of the SDS for the natural logarithm of 17-OHP. The primary analysis is focused on the change from baseline to week 24 in the primary efficacy variable.

The SDS is defined as the absolute (unsigned) number of standard deviations above or below the average of the lower and upper limit of normal.

The change from baseline to week 24 in the primary efficacy variable will be calculated in the following way:

- **Step 1: Calculate the SDS profile of log-transformed 17-OHP**

For each of the 13 concentrations at each visit (baseline, week 24), take the natural logarithm and then calculate the SDS by counting the number of standard deviations (given in Table 3) which are above or below the mean of the log transformed range (given in Table 3).

- **Step 2: Calculate the mean of the SDS profile**

Calculate the arithmetic mean over all 24-hour SDSs at each visit with the first and last observations weighted one half relative to the intermediate observations, e.g. for 13 observations ( $n_1, \dots, n_{13}$ ) this is calculated by  $(\frac{1}{2}n_1+n_2+\dots+n_{12}+\frac{1}{2}n_{13})/12$ . Lower values of the mean of the SDS profile should be interpreted as “better” hormonal control.

- **Step 3: Change from baseline to 24 weeks**

Take the natural logarithm of the mean of the SDS profile for the week 24 visit and subtract the natural logarithm of the mean of the SDS profile for the baseline visit. Negative values of this result should be interpreted as an improvement in hormonal control compared with baseline.

Table 2: Normal reference ranges for 17-OHP and A4

	Male	Female
17 OHP	1.2* – 6.7 nmol/L	1.2* – 8.6 nmol/L
A4	1.4 - 5.2 nmol/L	1.0 – 7 nmol/L

Source: Mayo Clinic.

17-OHP: <http://www.mayomedicallaboratories.com/test-catalog/Clinical+and+Interpretive/9231>.

Please note the upper reference range for females is during the Luteal phase.

\*There is no lower reference range available for 17-OHP, hence the lower limit of the optimal range (provided in Table 7) will be used in the derivation of the average SDS score. This will enable calculation of an 'unsigned' SDS score which can be used to assess potential overtreatment as well as undertreatment.

A4: <http://www.mayomedicallaboratories.com/test-catalog/Clinical+and+Interpretive/9709>

Table 3: Mean and SD of normal log-transformed range

Analyte	Sex	mean of log e -transformed range [ log e (nmol/L) ]	SD of log e -transformed range [ log e (nmol/L) ]
17-OHP	Male	1.042	0.430
	Female	1.167	0.492
A4	Male	0.993	0.328
	Female	0.973	0.486

Source: Mayo Clinic.

17-OHP: <http://www.mayomedicallaboratories.com/test-catalog/Clinical+and+Interpretive/9231>.

Please note the upper reference range for females is during the Luteal phase.

A4: <http://www.mayomedicallaboratories.com/test-catalog/Clinical+and+Interpretive/9709>

The mean of the "normal" log-transformed range was calculated by taking the natural logarithm of the upper and lower limit given in Table 2, calculating the range of the log-transformed values and finding the midpoint of the range. The SD of the log-transformed range was approximated by dividing the range of the log-transformed values by four.

### 9.2.3. Conversion factors

For the conversion of standard glucocorticoid replacement therapy to hydrocortisone, the conversion factors (Finkelstein 2012) are given in Table 4.

*Table 4: Conversion factors for standard glucocorticoid replacement therapy to hydrocortisone*

Standard glucocorticoid replacement therapy	Conversion factor
Prednisone or prednisolone	5
Dexamethasone	80 (up to a maximum starting dose of Chronocort® 30mg, split as 20mg at night and 10mg in the morning)

*Note: The conversion factor for Chronocort® is 1.*

For example, if a subject was previously taking 6mg daily of prednisone daily, this would be multiplied by a conversion factor of five and the equivalent hydrocortisone daily dose would be 30mg.

If a subject was previously taking prednisone in combination with hydrocortisone, then a conversion factor of five would be applied to the prednisone component of the dose, and a conversion factor of one would be applied to the hydrocortisone component of the dose, and the two added together.

All laboratory results will be reported in SI and conventional units. If for any reason the results are not collected in SI or conventional units, a conversion will be performed. Examples of some conversions to SI units are given in Table 5.

*Table 5: SI unit conversions*

Quantity	Conversion to SI units		
17-OHP	1 ng/dL	= 0.0303	nmol/L
ACTH	1 pg/mL	= 0.22	pmol/L
Androstenedione	1 ng/dL	= 0.0349	nmol/L
Glucose	1 mg/dL	= 0.0555	mmol/L
Insulin	1 µIU/mL	= 6.945	pmol/L
Osteocalcin	1 µg/L	= 0.171	nmol/L
PRA	1 NG/ML/HR	= 0.2778	NG/L/S

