## **Baseline Assessment and Randomisation (2-day visit)**

Subjects will be called in for the Baseline Visit (Visit 1) and admitted overnight for a 24-hour endocrine profile whilst remaining on their standard therapy. Subjects will have 17-OHP and A4 measured at 13 time points. On the second morning baseline bloods will be taken together with all safety measures and all secondary endpoint measurements (see Section 11).

After the completion of the baseline profile, the subject will be randomised either to receive Chronocort® or to continue on standard care. 120 subjects will be randomised (see Section 11).

The initial dose setting at the start of Chronocort® treatment will be made on hydrocortisone dose equivalent of baseline therapy, with the hydrocortisone dose calculated as prednisone dose multiplied by 5 and dexamethasone dose multiplied by 80 (up to a maximum starting dose of Chronocort® 30mg, split as 20mg at night and 10mg in the morning) Chronocort® will be given at 23:00 hours (approximately 2/3rd of the total daily dose) and 07:00 hours (approximately 1/3rd of the total daily dose). The first dose of Chronocort® will be taken at 23:00 hours on Day 2 of the baseline visit. Subjects will be asked to write on the pack the dose, date and time they took the first dose of study medication (Chronocort® or standard therapy).

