**Section 9.2.3 Conversion factors:**

Included Finkelstain 2012 reference for conversion factors used.

Added restriction for Dexamethasone conversion to Chronocort® from Protocol Version 4.0 in Table 4.

Updated text to state that laboratory data will be presented in both SI and conventional units.

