#### 10.7.4. Use of glucocorticoids

Use of glucocorticoids at visit 1 (baseline) and visit 4 (week 24) of the study will be presented as individual glucocorticoids used. Change in dose of last glucocorticoid from baseline to each visit will be presented as hydrocortisone equivalents using accepted conversion constants for the calculations (see Section 9.2.3).

A summary of the frequency and percent of subjects with total hydrocortisone dose equivalent increments versus baseline at each visit falling within the following categories:

- Dose increases versus baseline:
  - No increase observed ( $\leq 0$ mg),
  - $> 0$  to  $\leq 5$ mg increase,
  - $> 5$  to  $\leq 10$ mg increase,
  - $> 10$  to  $\leq 15$ mg increase,
  - $> 15$  to  $\leq 20$  mg increase,
  - $> 20$  to  $\leq 25$  mg increase,
  - $> 25$  to  $\leq 30$  mg increase and
  - $> 30$  mg increase.
- Dose decreases versus baseline:
  - No decrease observed ( $\leq 0$ mg),
  - $> 0$  to  $\leq 5$ mg decrease,
  - $> 5$  to  $\leq 10$ mg decrease
  - $> 10$  to  $\leq 15$ mg decrease,
  - $> 15$  to  $\leq 20$  mg decrease,
  - $> 20$  to  $\leq 25$  mg decrease,
  - $> 25$  to  $\leq 30$  mg decrease and
  - $> 30$  mg decrease.

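### SAP Table 4 puts the Chronocort starting-dose limit inside the dexamethasone conversion factor, so the exploratory hydrocortisone-equivalent dose summaries can be programmed in two ways

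*SAP*

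**What the plan says.** Table 4 in SAP Section 9.2.3 is titled "Conversion factors for standard glucocorticoid replacement therapy to hydrocortisone". It has two entries. Prednisone or prednisolone has a factor of 5 with no limit. The dexamethasone entry reads "80 (up to a maximum starting dose of Chronocort® 30mg, split as 20mg at night and 10mg in the morning". A note gives Chronocort a factor of 1. The SAP has no other dexamethasone factor.

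Section 10.7.4 uses this table. Change in dose from baseline to each visit is "presented as hydrocortisone equivalents using accepted conversion constants for the calculations (see Section 9.2.3". The same section plans "A summary of the frequency and percent of subjects with total hydrocortisone dose equivalent increments versus baseline at each visit", in 5 mg bands listed separately for increases and decreases. Both outputs are in the SAP's list of planned tables, and Protocol Section 13.6.3 lists the comparison of equivalent doses among the exploratory analyses.

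The limit comes from Protocol Section 8 (Baseline Assessment and Randomisation): "The initial dose setting at the start of Chronocort® treatment will be made on hydrocortisone dose equivalent of baseline therapy". There, and in Protocol Section 10.2.2, it bounds the first Chronocort prescription. The amendment history for Protocol Version 4.0 justifies it on dosing-safety grounds. The SAP revision history for Version 2.0 records how it reached the analysis table: "Added restriction for Dexamethasone conversion to Chronocort® from Protocol Version 4.0 in Table 4".

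**The concern.** A limit on what may first be prescribed of the new drug says nothing about how much steroid a subject was taking on the old one. With the limit in the same cell as the factor, a programmer who follows Table 4 to the letter will understate the baseline equivalent of every subject on more than 0.375 mg of dexamethasone a day. The SAP never says that the limit is to be ignored when doses are summarised.

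The error would also differ by arm. For Chronocort subjects who came from dexamethasone, only the baseline could be capped, because Chronocort converts at 1 without a limit. For controls who stay on dexamethasone, both ends of the change could be capped. All affected subjects fall in one randomisation stratum, so a summary by stratum would concentrate the distortion there.

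At stake is the description of dose change in each arm, which readers will set beside the hormonal results.

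**Working it through.** **Inputs.** Factors 5, 80 and 1, and the 30 mg limit: SAP 9.2.3. Usual dexamethasone adjustment step of 0.25 mg: Protocol Section 8, Dose Adjustment. Dose bands: SAP 10.7.4. The dexamethasone doses below and the later 35 mg Chronocort dose are illustrative assumptions. All doses are treated as daily totals.

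**Reproducing the SAP's own example.** The SAP says that "if a subject was previously taking 6mg daily of prednisone daily, this would be multiplied by a conversion factor of five": 6 × 5 = 30 mg, as stated. No converted dexamethasone figure is given to check.

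**Where the limit starts to act.** 30 / 80 = 0.375 mg a day.

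**Equivalent dose under the two readings.** Uncapped = 80 × dose; literal = the smaller of 80 × dose and 30.

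| Dexamethasone, mg/day | Uncapped, mg | Literal, mg | Understated by |
|---|---|---|---|
| 0.25 | 20 | 20 | 0 |
| 0.5 | 40 | 30 | 10 mg (25%) |
| 0.75 | 60 | 30 | 30 mg (50%) |
| 1.0 | 80 | 30 | 50 mg (62.5%) |

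**Change from baseline, Chronocort arm.**
- 0.5 mg to Chronocort 30 mg: 30 − 40 = −10 mg uncapped; 30 − 30 = 0 literal. In the decrease list the subject moves from the band above 5 and up to 10 mg to the no-decrease band. The entry in the increase list is the same either way.
- 0.5 mg to Chronocort 35 mg: 35 − 40 = −5 mg uncapped; 35 − 30 = +5 mg literal. The sign reverses.
- 0.75 mg to Chronocort 30 mg: 30 − 60 = −30 mg uncapped; 0 literal.

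For a baseline dose d above 0.375 mg, the literal change exceeds the uncapped change by 80d − 30, which is always positive. In this arm the literal reading can only make Chronocort look less dose-sparing.

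**Change from baseline, controls on dexamethasone, if the limit is applied to them as well.**
- 0.25 to 0.5 mg: +20 mg uncapped; 30 − 20 = +10 mg literal.
- 0.5 to 0.75 mg: +20 mg uncapped; 0 literal.
- 0.75 to 0.5 mg: −20 mg uncapped; 0 literal.

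Here increases and decreases are both hidden, so the direction is not fixed.

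**Possible effect on a mean.** Assume that a share s of subjects takes dose d above the threshold. The mean baseline equivalent is then understated by s × (80d − 30). With s from 5% to 30% and d from 0.5 to 0.75 mg, this runs from 0.05 × 10 = 0.5 mg to 0.30 × 30 = 9 mg. The range shows only how strongly the result depends on figures that the documents do not give.

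**The case against.** The strongest reply is that the cell gives the factor as 80 and the bracket merely repeats a prescribing rule. A night and morning split makes sense only for a prescription, the bracket names a Chronocort starting dose, and the revision history calls it a restriction on conversion to Chronocort. Section 10.7.4 asks for accepted constants, and the constant is 80. This stands as a plausible reading, which is why truncation is the literal result and not a certainty. It does not remove the defect, because the table is headed as an analysis conversion and nothing tells the programmer to drop the bracket.

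The control-arm case is weaker still. A control never starts Chronocort, so capping that subject goes against the bracket's own words. That reading is less likely, but the table draws no distinction by arm or visit and so does not exclude it.

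A reader might infer that the plan will conceal true steroid exposure and so undermine a central steroid-sparing claim. The documents do not support that:
- Glucocorticoid use is an exploratory endpoint, and no listed objective concerns glucocorticoid dose. The protocol's statement about control without greater exposure describes the phase II study.
- Section 10.7.4 also presents baseline and week 24 use by individual glucocorticoid, and dosing is listed, so dexamethasone changes remain visible in mg.
- The uncapped changes are not true values in any absolute sense. They depend on the factor of 80, and the amendment history acknowledges that clinicians use different factors.

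**Conclusion.** The point holds in a limited form: Table 4 is ambiguous as an analysis instruction, and its literal reading gives wrong dose changes for subjects on more than 0.375 mg of dexamethasone a day. At the illustrative doses, the error per subject in the Chronocort arm is 10 mg from a 0.5 mg baseline and 30 mg from 0.75 mg, with a possible change of sign. The effect on arm or stratum means is unknown, because the documents give neither the dexamethasone dose distribution nor the size of that stratum.

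Two related gaps remain. For dexamethasone combined with another glucocorticoid, the SAP does not say whether the limit would fall on the dexamethasone part or on the total. The change summary in 10.7.4 refers to the last glucocorticoid dose, which may be a single dose and not a daily total; the figures above assume daily totals.

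The primary 17-OHP analysis, the A4 and responder analyses and compliance do not use the factor. This is a minor but real correction.

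**What to change.** In Table 4, give the dexamethasone analysis factor as 80 and delete the bracket. Add one sentence: the protocol's limit on the Chronocort starting dose is not applied to any hydrocortisone-equivalent dose in Section 10.7.4, at baseline or later, in either arm. Say that combinations containing dexamethasone are converted component by component and summed, as the SAP already does for prednisone with hydrocortisone. If the SAP needs to mention the limit, place it in Section 3 as a description of the protocol's dose-setting rule.

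The cost is one table cell and two sentences. No data collection, dosing rule or other planned analysis changes. If the tables have already been programmed, check which reading was used and state it in the study report.
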